All cases will be managed according to the sponsor's Pharmacovigilance processes, in line with the applicable legislation.

Whenever applicable, individual case safety reports (ICSRs) will be submitted to Health Authorities on an expedited basis according to current regulations.

Progress status updates will be given in each Periodic Safety Update Report (PSUR) and Development Safety Update Report (DSUR) if applicable.

Additionally, a descriptive analysis of the data collected will be provided annually in the PSUR.

Study duration and dates

Recruitment of women will be done using a website access. Implementation of the website is planned for the second quarter of 2014 and website will be in place during the whole course of the study.

STUDY SCHEDULE

Period of pregnancy Study procedures	Enrolment in the study	Pregnancy Course	End of pregnancy	4 months FU ³
Written ¹ informed consent	X			
Inclusion criteria	X			
Pregnancy diagnosis	X			
ella [®] exposure	X			
Prior and concomitant medications	X	X	X	
Recreational drug use (tobacco, alcohol, illicit drugs)	X	X	X	
Serology and prenatal tests results	X			
Medical history	X			
Maternal and fetal pregnancy complication	X	X	X	
Pregnancy outcome ²			X	
Live birth follow-up ³				X

¹: Signed ICF will be collected according to local regulations. When completed by the HCP, prior starting the questionnaire completion, the ICF will be downloaded from the website and a print-out copy signed by the woman. When completed by the woman, prior starting the questionnaire completion, an electronic signature will be requested on the ICF module and the woman will be requested to save and/or print the ICF for her records.

²: Possible pregnancy outcomes are: Live birth (healthy baby, congenital anomaly or other neonatal diagnosis, or neonatal death); pregnancy loss (spontaneous abortion or ectopic pregnancy or induced abortion, premature stillbirth)

³: In case of live birth, the period of observation of the study will last for 4 months post-delivery to access possible congenital anomalies that may not be detected at birth.

ABBREVIATIONS AND DEFINITIONS

ADR	Adverse Drug Reaction
AE	Adverse Event
AFP	Alpha-Fetoprotein
CFR	Code of Federal Regulations
CHMP	Committee for Medicinal Products for Human Use
CRO	Contract Research Organization
DMB	Data Monitoring Board
DSUR	Development Safety Update Report
EC	Emergency Contraception
EUROCAT	European Surveillance of Congenital Anomalies

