2.2 Secondary objectives

The secondary objectives of this observational study are:

- To collect data on fetal and neonatal outcomes, birth and maternal complications in pregnancies exposed to ella®;
 - To assess the nature and incidence of complications of pregnancy loss in pregnancies exposed to ella®.

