8 STUDY PROCEDURES AND SCHEDULE

8.1 Overview of safety data

Pregnancy information

Date of diagnosis, date of LMP, date and results of ultrasound (if applicable) and expected delivery date.

Exposure to ella®

Data on exposure to ella® include date of ella® intake and number of tablets taken, time from intercourse to ella® intake; pregnancy stage at ella® exposure, pregnancy status before ella® intake.

Outcomes

All outcomes and the data collected to assess them are:

- Live birth – gender, birth weight, gestational age, delivery method and Apgar scores will be collected in all cases. For healthy babies and those with congenital anomalies or other neonatal diagnosis, the study observation period will last until 4 months after delivery;
 - Congenital anomaly or other neonatal diagnosis – description of anomaly and possible causes will be additionally collected;
 - Neonatal death (from birth through to 28 completed days of age*) – age at death, possible etiology and result of autopsy if performed will be additionally collected.
- Pregnancy loss – gestational age, possible etiology of pregnancy loss and any complications (vaginal bleeding, need for curettage, infection) will be collected in all cases.
 - Spontaneous abortion (or early fetal death i.e. < 20 completed weeks of gestation*)
 - Ectopic pregnancy
 - Induced abortion (no medical reason – woman's elective choice, elective abortion with fetal defects, or maternal health complications)
 - Stillbirth:
 - Intermediate fetal death (more than 20 completed weeks of gestation but less than 28*)
 - Late fetal death (\geq 28 completed weeks of gestation*).

Maternal health complications of pregnancy

In all cases, relationship of the outcome observed with the exposure to ella® will be assessed by the HCP and according to the standard pharmacovigilance process.

* According to the WHO International Classification of Disease (ICD)

Prior and concomitant medications

Prior and concomitant medications will be collected in the HCP or women questionnaires. Collection period covers the pregnancy duration from LMP to the end of pregnancy.

Other

Maternal family history; recreational drug use (tobacco, alcohol, illicit drugs) and serological and prenatal tests.

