8.2.1.3 Completion of the Pregnancy Outcome Forms

When the outcome of the pregnancy is known*, the HCP will be asked to fill-in the Pregnancy Outcome forms.

- Access the website with the HCP unique user ID and password
- Start the Pregnancy Outcome Form completion
- Collect the pregnancy outcome observed [live birth (i.e. healthy baby, congenital anomaly, neonatal death) including pregnancy complications, pregnancy loss (including spontaneous abortion, ectopic pregnancy, therapeutic abortion, intermediate or late fetal death), maternal health complications]
- Collect recreational drug use (tobacco, alcohol, illicit drugs), if any
- Collect relevant maternal and family medical history, including history related to previous pregnancies, including congenital birth defects
- Collect serology and prenatal tests (type, date, results)
- Collect relevant concomitant medications
- Save and submit the forms.

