9.2.2.2 Primary Objective Assessments

The primary objective of this observational study is to estimate the rates of occurrence of outcomes of pregnancies exposed to ella® in order to detect a possible signal of concern for adverse outcomes related to exposure to ella®.

Each pregnancy outcome will be described by proportions (cumulative incidence/prevalence) with exact 95% confidence interval.

For each pregnancy outcome, data from all sources (past and current clinical trials, registry, spontaneous pharmacovigilance reporting) will be used. Outcomes to be evaluated are defined as follows:

All Induced abortions (due to a medical/non-medical reason):

Proportion of normal-appearing pregnancies (with analysable ultrasound results) before induced abortion = number of normal-appearing pregnancies with ultrasound compatible with normal growth and development/ number of pregnancies with analysable ultrasound results.

Therapeutic abortion (medical indication)

Proportion of therapeutic abortions = number of therapeutic abortions / number of pregnancies

Birth outcomes

Proportion of live births = number of live births/ total number of births

Proportion of healthy babies = number of live births without any anomaly (healthy babies) / number of deliveries

Total live birth prevalence of congenital anomalies = number of live births with congenital anomalies / number of live births

Proportion of neonatal deaths = number of neonatal deaths / number of live births

Congenital anomalies:

Total prevalence of congenital anomalies = total number of congenital anomalies (terminations of pregnancy for fetal anomaly (TOPFA), stillbirths, live births with congenital anomalies / total number of births (live births + stillbirths)

Pregnancy loss outcomes

Proportion of spontaneous abortions (or spontaneous abortion cumulative incidence) = number of spontaneous abortions / number of pregnancies

Proportion of intermediate fetal deaths* = number of intermediate fetal deaths / number of pregnancies

Proportion of stillbirths (or stillbirth cumulative incidence) = number of stillbirths / number of pregnancies

* more than 20 completed weeks of gestation but less than 28, according to the WHO fetal death classification.

Proportion of ectopic pregnancies (or ectopic pregnancy cumulative incidence) = number of ectopic pregnancies / number of pregnancies with known outcomes reported

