9.2.2.3 Secondary Objective Assessments

The secondary objectives of this observational study are to:

- Collect data on pregnancy, birth and maternal complications in case of pregnancies exposed to ella®.
- In addition to statistical analysis, pregnancy, birth and maternal complications will be described with a case by case approach, and the relationship with ella® intake (certain / probable / possible / unlikely / not related / unknown) will be assessed by pregnancy data monitoring board (DMB).
- Assess the nature and incidence of complications of pregnancy loss in pregnancies exposed to ella®.

Complications of pregnancy loss are of special interest, in particular excessive and prolonged bleeding events.

Duration of bleeding events will be described in terms of descriptive statistics (mean, standard deviation, median, range).

The cumulative incidence of excessive bleeding episodes (considered as excessive by the HCP) will be calculated by dividing their occurrence by the number of pregnancy losses during the study.

Cumulative incidence of maternal health complications related to pregnancy loss will also be calculated by dividing the number of complications by the number of pregnancy losses.

These proportions (cumulative incidence) of adverse events and their 95% confidence intervals will be calculated for the overall sample as well as by country, in order to assess potential differences due to variations in clinical practice regarding the management of pregnancies and pregnancy complications. Results will also be presented by age.

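### Complications of pregnancy loss are divided by a number of pregnancy losses that the protocol defines in different ways, and no split by type of loss is planned, so the incidence depends on the share of terminations

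*Protocol*

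**What the plan says.** The secondary objective in Protocol section 2.2 is "To assess the nature and incidence of complications of pregnancy loss in pregnancies exposed to ella". Section 9.2.2.3 turns it into formulas. Bleeding considered excessive by the health care professional is summarised "by dividing their occurrence by the number of pregnancy losses during the study", and maternal complications related to the loss "by dividing the number of complications by the number of pregnancy losses". Duration of bleeding gets summary statistics. Results are shown overall, by country and by age. No breakdown by type of loss is stated, and section 9.2.2.3 does not define a pregnancy loss.

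Other sections do describe the category, in different ways:

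- Study schedule, footnote 2: "pregnancy loss (spontaneous abortion or ectopic pregnancy or induced abortion, premature stillbirth".
- Section 8.1: one entry under pregnancy loss begins "Induced abortion (no medical reason" and goes on to the woman's own choice, fetal defects and maternal health. For losses, "any complications (vaginal bleeding, need for curettage, infection) will be collected in all cases".
- Section 8.2.1.3 (form for the health care professional): "pregnancy loss (including spontaneous abortion, ectopic pregnancy, therapeutic abortion, intermediate or late fetal death". Section 8.2.2.2 (form for the woman) has the same list.
- Section 9.2.2.2: "All Induced abortions (due to a medical/non-medical reason" is a heading of its own, and so is therapeutic abortion. The pregnancy loss group there contains only spontaneous abortion, intermediate fetal death, stillbirth and ectopic pregnancy.

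**The concern.** There are two linked problems.

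First, the denominator is not fixed. Depending on the section followed, it contains all induced abortions, only therapeutic ones, or none. Two analysts could report different incidences from the same data and each cite the protocol.

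Second, under the widest definition the incidence is an average over events of different kinds. Bleeding and other complications after a termination need not occur at the same rate as after a miscarriage, an ectopic pregnancy or a fetal death. The average then shifts with the proportion of women who had a termination, even if no risk has changed.

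Section 9.2.2.3 singles out excessive and prolonged bleeding as of special interest, so a diluted figure matters there. The country breakdown is meant to show differences in clinical practice. Without type of loss, a difference between countries in the share of terminations would look like a difference in complication risk. The country breakdown is relevant although enrolment is in the USA, because section 9.2.1 pools these data with all other reports held by the sponsor.

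**Working it through.** The protocol states no figure on this point, so there is none to reproduce. The check has two parts.

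**1. The definitions side by side**

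| Place in the protocol | Elective abortion in pregnancy loss? | Therapeutic abortion in pregnancy loss? |
|---|---|---|
| Study schedule, footnote 2 | yes (induced abortion, unqualified) | yes |
| Section 8.1 | yes, stated | yes, stated |
| Sections 8.2.1.3 and 8.2.2.2 | not named | yes |
| Section 9.2.2.2 | no (separate heading) | no (separate heading) |
| Section 9.2.2.3 | not defined | not defined |

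The lists in 8.2.1.3 and 8.2.2.2 are introduced as inclusive, so they may not be complete. Section 9.2.2.2 cannot be reconciled with 8.1 in that way.

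**2. How far the mix can move the figure**

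Let w be the share of losses that are induced abortions, p_i the complication risk in them, and p_s the risk in the other losses:

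pooled incidence = w × p_i + (1 − w) × p_s

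The protocol gives none of these three quantities. All values below are assumptions.

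*Dilution of a signal.* Take p_s = 15% and p_i = 3%, and let p_s double to 30% with p_i unchanged.

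- w = 50%: 0.5 × 3 + 0.5 × 15 = 9.0%; after doubling, 0.5 × 3 + 0.5 × 30 = 16.5%; ratio 16.5 / 9.0 = 1.83.
- w = 80%: 0.8 × 3 + 0.2 × 15 = 5.4%; after doubling, 0.8 × 3 + 0.2 × 30 = 8.4%; ratio 8.4 / 5.4 = 1.56.

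The true ratio in non-induced losses is 2 in both cases. These ratios further assume a comparator with the same induced share and no exposure effect in induced abortions.

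*Effect of the definition.* With the same baseline risks, an analyst who leaves induced abortions out (w = 0) reports 15%. One who includes them, at w = 50%, reports 9.0%. The therapeutic-only reading lies in between.

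*Country comparison.* Two countries with identical risks by type, one with w = 50% and one with w = 80%, would show 9.0% and 5.4%. The ratio is 9.0 / 5.4 = 1.67, with no difference in risk for either type of loss.

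*Other assumed rates.* With p_s = 10% and p_i = 2%, the pooled figure is 8.0%, 6.0%, 4.0% and 2.8% for w = 25%, 50%, 75% and 90%. With 5% in both groups it stays at 5% whatever w is, so pooling is harmless when the risks are equal.

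*Precision after a split.* Assume 100 losses, half of them induced, at the 10% and 2% rates. The events are 5/50 and 1/50, together 6/100. The protocol's own Table 3 gives the exact 95% intervals:

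| Group | Events | Estimate | 95% interval |
|---|---|---|---|
| All losses | 6/100 | 6.0% | 2.2 to 12.6% |
| Non-induced | 5/50 | 10.0% | 3.3 to 21.8% |
| Induced | 1/50 | 2.0% | 0.05 to 10.6% |

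**The case against.** The strongest reply is that section 9.2.2.2, immediately before the formulas, already separates induced abortion from pregnancy loss. If 9.2.2.3 inherits that grouping, terminations are not in the denominator and the dilution does not arise. This is a fair reading, and it is why the inclusion of induced abortions cannot be stated as fact. It does not remove the point. Section 8.1, which sets out the outcomes for data collection, says the opposite, and 9.2.2.3 does not say which applies.

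A second reply is that section 9.2.2 leaves detail to the statistical analysis plan, which is not at hand and could add a table by type. That would be enough if the protocol were silent, but 9.2.2.3 itself fixes the formula and lists the breakdowns.

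A third is that complications are also described case by case, with causality assessed by the data monitoring board. That gives protection for individual cases, but it yields no incidence by type of loss.

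A reader might go further than the text allows in four ways:

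- *That the secondary objective is left unanswered.* The objective concerns pregnancy loss, not miscarriage. An all-loss incidence answers it literally; the difficulty is interpretation.
- *That routine procedural bleeding is counted as a complication.* The bleeding incidence counts only episodes judged excessive by the health care professional, which may already exclude expected bleeding. The duration summary has no such filter.
- *That planned curettage inflates the figure.* Section 9.2.2.3 does not mention curettage. Section 8.1 lists the need for it as a complication, and nowhere is a planned surgical abortion said to be coded as one.
- *That terminations dominate because most women enrolled are treatment failures.* Section 4.3 admits treatment failure and inadvertent exposure alike and gives no proportions.

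**Conclusion.** The point holds in a limited form. The denominator in 9.2.2.3 differs by reading, because the protocol uses pregnancy loss inconsistently. Under the definitions in the study schedule footnote and section 8.1, the planned incidence pools induced abortion with other losses, varies with the share of terminations, and can blur a bleeding signal or the comparison between countries.

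The size cannot be derived from the protocol. The ratios of 1.83 and 1.56 in place of 2 illustrate the mechanism under assumed risks and shares. They do not estimate the bias in this study, and with equal risks there would be none. The point merits correction because the remedy is cheap and removes the ambiguity under every reading. It does not invalidate the objective or the data collection.

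**What to change.** 1. Define pregnancy losses once, state whether elective and therapeutic abortions belong, and use that definition in the study schedule footnote and in sections 8.1, 8.2.1.3, 8.2.2.2, 9.2.2.2 and 9.2.2.3.
2. In 9.2.2.3, report bleeding duration, excessive bleeding and complication incidence at least separately for induced abortion and for non-induced losses. Give each incidence over the number of losses in its own group. Show spontaneous abortion, ectopic pregnancy and fetal death by type where numbers allow.
3. Keep the all-loss figure as a supplement, and give the share of induced abortions beside it, by country as well, so that the mix is visible.

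Which type of loss should carry most weight for the objective is the sponsor's choice and need not be settled to make this change. Type of loss is already collected, so the change needs only wording in the protocol and the matching text in the analysis plan. The price is precision: in the example above the interval runs from 3.3 to 21.8% for 5/50, against 2.2 to 12.6% for 6/100. Smaller groups would be less precise still, which is why the finer split is conditional on numbers.

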8.3 Participant follow-up

Reporters (HCP or women) will be asked to carefully keep either their user ID and password or the unique patient number they received.

Reporters, mainly the HCP can be contacted by the Sponsor's drug safety department to obtain medical follow-up information on women included in the study or on baby(ies)'s health 4 months after the delivery date (for live births only).

However, as stated earlier, if the reporter is a woman who did not provide contact details of an HCP the system will generate an e-mail to the woman to request further information. Note that the woman email address will be kept blinded to the sponsor.

Additionally, each HCP having enrolled a woman before the pregnancy outcome was known will be contacted by the Sponsor's drug safety department at 20 weeks of the pregnancy and at the scheduled delivery date and will be asked to complete the online questionnaire accessible on the website.

This contact will be done via e-mail within 15 days after the presumed date of delivery. If no answer is received within 30 days, the HCP will be contacted again twice with 1 month interval.

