9.2.2.1 Descriptive analysis

Descriptive statistics (mean, standard deviation, 95% confidence interval for mean, minimum, median, maximum, and number of observations and missing cases) for quantitative variables, and proportions (cumulative incidence or prevalence) for categorical variables will be calculated with binomial or Poisson exact confidence intervals. The proportion of cases that are lost to follow-up will be described.

Baseline characteristics data of enrolled and completed cases will be described: age, pregnancy status at time of ella® exposure, time from unprotected intercourse to exposure in case of treatment failure, or time from LMP to exposure in case of inadvertent use as well as multiple ella® intakes since her LMP.

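### Section 9.2.2.3 divides complications by pregnancy losses and calls the result a proportion; if types are pooled or repeats counted, this is events per loss, so the numerator should be losses with at least one complication

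*Protocol*

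**What the plan says.** Protocol section 9.2.2.3 gives two formulas for the second secondary objective, the nature and incidence of complications of pregnancy loss.

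- **Maternal complications of loss:** the cumulative incidence is found by "dividing the number of complications by the number of pregnancy losses".
- **Excessive bleeding:** "The cumulative incidence of excessive bleeding episodes (considered as excessive by the HCP) will be calculated by dividing their occurrence". The denominator is again all losses in the study.

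The section then names the results "These proportions (cumulative incidence) of adverse events and their 95% confidence intervals". They are to be given overall, by age, and "by country, in order to assess potential differences due to variations in clinical practice regarding the management of pregnancies and pregnancy complications".

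Three other places bear on the reading:

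- Section 8.1, for every pregnancy loss: "any complications (vaginal bleeding, need for curettage, infection) will be collected in all cases".
- Section 9.2.2.1, on intervals: proportions "for categorical variables will be calculated with binomial or Poisson exact confidence intervals". It does not say which interval belongs to which measure.
- Section 9.2.2.2, for live-birth prevalence of anomalies: "number of live births with congenital anomalies / number of live births". Here the numerator counts affected units.

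**The concern.** A cumulative incidence is the share of units at risk that are affected, so its numerator must be a subset of its denominator. Complications are not a subset of losses. Bleeding, curettage and infection can all follow the same loss, and section 9.2.2.3 has no rule that a loss counts once. Followed literally for complications taken together, the formula gives a mean count per loss under the name of a proportion.

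These are the aggregate estimates for a stated secondary objective, and the section singles these complications out as of special interest. The country breakdown is meant to reveal differences in clinical practice. Two countries with the same share of losses affected would look different if affected losses in one of them carried more complications each.

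**Working it through.** **Plan's own figure.** The protocol states no value for this measure, so there is none to reproduce. As a check of the interval method, the exact binomial interval for 80/400 is 16.2-24.3%, which matches Annex 1, Table 3.

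**Algebra.** Let L be pregnancy losses, A losses with at least one complication, C complications, and m = C/A the mean number of complications per affected loss.

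- Share of losses affected: A/L.
- Formula as written: C/L = (A/L) × m.

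The two agree only when m = 1. Otherwise the formula overstates the share by the factor m, whatever the number of losses.

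**Illustration; the counts are assumed.** The protocol gives no number of losses, no complication rate and no m. For a base, take 400 pregnancies (section 4.1) × 20% miscarriage baseline (section 9.1) = 80 losses. Other kinds of loss have no stated rate, but the factor m does not depend on the base. Assume A = 16.

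- True share: 16/80 = 20.0% (exact 95% CI 11.9-30.4).
- Formula at m = 1.25: 20/80 = 25%.
- Formula at m = 1.5: 24/80 = 30.0% (exact binomial CI 20.3-41.3).
- Formula at m = 2: 32/80 = 40%.

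**Pooling three types, with assumed per-loss risks.** Events per loss is the sum of the risks. The share affected is 1 minus the product of (1 − risk) if types are independent, and the largest risk if they are fully nested.

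| Risks of the three types | Events per loss | Share affected, independent | Share affected, nested |
|---|---|---|---|
| 5%, 5%, 2% | 12.0% | 11.6% | 5.0% |
| 20%, 15%, 5% | 40.0% | 35.4% | 20.0% |
| 50%, 40%, 20% | 110% | 76% | 50% |

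The gap is negligible when complications are rare and independent. It is large when they are common or cluster in the same losses.

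**Small country stratum (assumed).** 12 complications in 10 losses gives 12/10 = 120%. No binomial interval exists for this. The exact Poisson interval is 0.62-2.10 events per loss, which is an interval for a rate and not for a proportion.

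**Country contrast (assumed).** With 20% of losses affected in both countries and m = 1 and 1.5, the table would show 20% × 1 = 20% and 20% × 1.5 = 30%.

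**Excessive bleeding (assumed).** If 8 of 80 losses are affected and 2 of them have two episodes, 8/80 = 10.0% (exact CI 4.4-18.8) is reported as 10/80 = 12.5%. This arises only if one loss can have more than one episode judged excessive.

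**The case against.** **The protocol may simply be using shorthand.** In section 9.2.2.2 the total prevalence line also speaks of a number of anomalies, though one fetus can have several, and its bracket shows that affected cases are meant. The label of proportion in section 9.2.2.3 points the same way. This has weight as evidence of intent. But the bracket that settles the meaning there has no counterpart in section 9.2.2.3.

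**Pooling is not stated.** This stands. An objective about the nature as well as the incidence of complications may suggest reporting by type. By type, with each loss counted once, the ratio is a valid proportion. A reader might infer that the protocol plans a pooled figure that is bound to be inflated; the text does not say so.

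**Counting rules belong in the SAP.** Section 9.2.2 defers detail to the SAP, and omission of a counting rule would be no finding. Here, however, the protocol states numerator, denominator, label and interval, and taken literally they do not fit together. A general deferral does not undo a stated formula.

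**The exact Poisson option covers event counts.** It could serve an events-per-loss rate, though complications of one loss are not independent. It would not turn that rate into a proportion.

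**Other stronger readings.** One might conclude that the planned intervals would usually miss the true share. Any such coverage figure only restates the assumed m and is not separate evidence. One might also infer that bleeding incidence is distorted because a clinician judges it while section 8.3 provides for a case "if the reporter is a woman who did not provide contact details of an HCP the system will generate an e-mail to the woman". The protocol does not show how many losses would lack a clinical judgement, and section 4.2.2 offers a referent physician, so no such distortion can be asserted.

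**Conclusion.** The point holds in conditional form. As written, the formula does not deliver the quantity it names whenever types are pooled or a type is counted more than once per loss. It then gives events per loss, inflated over the share affected by the mean number of complications per affected loss, and unbounded by 100%. If each type is reported alone and each loss counted once, there is no error.

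The size in this study is unknown. The move from 20.0% to 30.0% rests on an assumed 16 of 80 losses affected and 1.5 complications per affected loss, and the country contrast rests on an assumed difference in multiplicity. The bleeding formula is affected only if episodes can repeat within a loss.

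The measure is secondary and descriptive. The primary outcomes, the sample size of 400 and the case-by-case review by the Data Monitoring Board do not depend on it. The change is worth making because it is nearly free and concerns the headline estimate for a stated objective.

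**What to change.** In section 9.2.2.3, define the numerators as:

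- pregnancy losses with at least one complication, overall and for each type;
- pregnancy losses with at least one excessive-bleeding episode.

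Divide each by the number of pregnancy losses and give exact binomial 95% confidence intervals. If the total number of complications is wanted, report it separately as a mean count per loss, not as a proportion.

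The cost is the wording of two numerators; no new data are needed. The downside is that a loss with several complications counts once in the overall figure, so multiplicity shows only in the per-type rows and in the mean count, if that is reported.
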